- Significant psychiatric illness or any other condition rendering the subject incapable of understanding the objectives and potential consequences of the study

Participants will be randomly assigned using a computer-generated random sequence at a 1:1 ratio to either the Telemedicine group or the Standard of Care (SoC) group. All participants will be followed for six months, unless they died or if they withdrew consent and decided not to

“Improving Glycemic Control in DM2 Patients in the Ambulatory Setting”

PI [name]
NCT04800471

continue participating in the study. No sample size calculations are provided due to the pilot nature of this study. Instead, we used a convenience sample of 30 subjects. This study was approved by the BVAMC IRB Committee.

Following consent, subjects in both groups will have a baseline research visit where they will be placed on a ("blinded") Dexcom G6 CGM device for ten days to obtain baseline CGM glucose data. A baseline assessment of PA will be obtained by completion of the Senior Fitness test. Subjects will be then randomized to either Telemedicine or the Standard of Care (SoC).

Participants in the telemedicine group will be educated about the appropriate use of the telemedicine system components. They will be asked to use their CGMs for ongoing automatic glucose monitoring, SIPs for insulin administration with recording insulin use, software applications, and VVC, SM, and telephone for telemedicine visits. Participants in the SoC will receive diabetes education as per standard of care (i.e., frequency of POC checking and proper insulin administration, among others). They will be asked to use POC for glucose monitoring and traditional insulin pens for insulin administration, and they will be asked to document POC, and insulin use as per standard of care.

Then, following the initial baseline visit, patients in the Telemedicine group will have the following interventions:

- i) in-person (Initial) Clinic Visit (Day 0):*

“Improving Glycemic Control in DM2 Patients in the Ambulatory Setting”

PI [name]
NCT04800471

This will be a typical in-person clinic visit. Vital signs, medications, and a medical history will be obtained. POC values will be reviewed, and DM medication adjustments will be performed. CBC, BMP, HbA1c, and urine creatinine/microalbumin will be obtained per usual care.

ii) Telemedicine visits (~every three weeks until +180 days [end of RCT]):

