iii) One Research Visit: This visit will be at +180 days (end of RCT) and will be identical to the research visit of the Telemedicine clinic group.

“Improving Glycemic Control in DM2 Patients in the Ambulatory Setting”

PI [name]
NCT04800471

Outcome Measures

The purpose of this trial will be to examine the feasibility of the above interventions (CGMs, SIPs, Telecommunication systems and promoting PA by EP) combined as a single telemedicine intervention and examine whether it can lead to improvement in hyperglycemia, as defined by a decrease in HbA1c (primary outcome). Secondary outcomes will be time in range (TIR) 70-180 mg/dL, time below range (TBR) <70 mg/dL, TBR <54 mg/dL, time above range (TAR \geq 180 mg/dL and TAR \geq 250 mg/dL. In addition, we will evaluate differences in hypoglycemic events (CGM glucose <70 mg/dL for at least 15 minutes), clinically significant hypoglycemic episodes (CGM glucose < 54 mg/dL for at least 15 minutes), and nocturnal hypoglycemia. For glucose variability, we will evaluate if there is a difference in the Coefficient of Variation (CV).

STATISTICAL ANALYSIS

Student's t-test will be used to compare baseline characteristics of the two groups. For continuous outcome measures (e.g., HbA1c, time <54 mg/dL, etc.), we will use linear regression analyses (SAS proc genmod with a normal distribution and identity link). For outcome measures that will be counts (e.g., number of hypoglycemic episodes <54 mg/dL), we will use Poisson regression (SAS proc genmod with a Poisson distribution and a log link). Regardless of the type of regression we will use, the model will be change in outcome= baseline value + group + time + group + time where group will be control or telemedicine and time will be baseline, three-month, or six-month. We will calculate estimated values at each time point using the mean value of the outcome at baseline, baseline value, (SAS LSMeans statement with a pdiff option). Comparisons of baseline

“Improving Glycemic Control in DM2 Patients in the Ambulatory Setting”

PI [name]
NCT04800471

characteristics will be performed using Student's t-test. A two-tailed $P \leq 0.05$ will indicate significance.

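### Hypoglycemic episode counts: a log-transformed baseline suits the log-link model better than the raw count, and LSMeans at the mean baseline should not be presented as arm means

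*Combined protocol and SAP*

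**What the plan says.** Under Statistical Analysis in the combined protocol and SAP, continuous outcomes get a normal model with identity link. For counts, "we will use Poisson regression (SAS proc genmod with a Poisson distribution and a log link"). One linear predictor serves both: "Regardless of the type of regression we will use, the model will be change in outcome= baseline value", plus group and time terms. The baseline is not transformed for counts.

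On reporting, the section states: "We will calculate estimated values at each time point using the mean value of the outcome at baseline", obtained through the "SAS LSMeans statement with a pdiff option". Averaging predictions over the patients' observed baselines is not mentioned.

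The counts are CGM-defined events listed under Outcome Measures after the primary and secondary outcomes, for example "clinically significant hypoglycemic episodes (CGM glucose < 54 mg/dL for at least 15 minutes"). The baseline count comes from a blinded "Dexcom G6 CGM device for ten days to obtain baseline CGM glucose data", and the blinded wear is repeated at +180 days. On size, "we used a convenience sample of 30 subjects", allocated 1:1. No event rate, dispersion or correlation is given.

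**The concern.** Under an identity link, a raw baseline is a natural covariate. Under a log link, it says that each extra baseline episode multiplies the expected follow-up count by the same factor, so predictions grow exponentially with the baseline count. If patients differ in an underlying event rate, follow-up counts should instead rise roughly in proportion to the baseline count plus a constant, which a log-type covariate matches. A poor covariate form wastes precision, and a trial of 30 has little to spare.

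The second issue is reporting. The exponential of an average is not the average of the exponentials. A log-link LSMean at the mean baseline is therefore not the arm's mean count, although readers may take it as each arm's hypoglycemia burden.

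**Working it through.** **Starting point.** The plan gives no figure to reproduce for this outcome. The document inputs are 30 patients at 1:1 (30/2 = 15 per arm), Poisson with log link, an untransformed baseline, and LSMeans at the mean baseline. Everything else below is assumed.

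**Step 1: the response.** A change in counts was negative for about 35-60% of patients in gamma-rate simulations, and a Poisson model cannot take negative values. The workable reading is the follow-up count as response. The rest uses that, with one follow-up count per patient.

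**Step 2: shape of the covariate.** Take baselines of 2, 5 and 10 episodes. If follow-up is proportional to baseline + 0.5, the expected count rises 5.5/2.5 = 2.2-fold from 2 to 5, and 10.5/2.5 = 4.2-fold from 2 to 10. A raw-count model that matches the first step (2.2-fold over 3 episodes) must predict 2.2^(8/3) = 8.2-fold for the second.

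**Step 3: precision.** Lognormal patient rates, rate ratio 0.6, about 6,000 simulated trials per setting. Results for a mean of 5 episodes per wear:

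| Log-SD of rates | Correlation | SD of log rate ratio: no covariate | Raw | Log(baseline + 0.5) | Raw/none | Cut, 1 - log/raw |
|---|---|---|---|---|---|---|
| 1.0 | 0 | 0.496 | 0.507 | 0.506 | 1.02 | 0.2% |
| 1.0 | 0.4 | 0.496 | 0.497 | 0.482 | 1.00 | 3.0% |
| 1.0 | 0.7 | 0.493 | 0.447 | 0.416 | 0.91 | 6.9% |
| 1.0 | 0.9 | 0.494 | 0.382 | 0.335 | 0.77 | 12.3% |
| 1.5 | 0 | 0.817 | 0.843 | 0.833 | 1.03 | 1.2% |
| 1.5 | 0.2 | 0.807 | 0.857 | 0.817 | 1.06 | 4.7% |
| 1.5 | 0.7 | 0.812 | 0.801 | 0.685 | 0.99 | 14.5% |
| 1.5 | 0.9 | 0.820 | 0.656 | 0.501 | 0.80 | 23.6% |

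At a mean of 2 the cuts are smaller at high correlation: at 0.9, 1 - 0.468/0.503 = 7.0% (log-SD 1.0) and 1 - 0.632/0.767 = 17.6% (log-SD 1.5).

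A gamma-rate grid (shape 0.5-2; 1, 4 or 8 episodes per wear; period noise SD 0 or 0.8; rate ratio 0.5; 18 settings of 1,500 trials) gave cuts of 2-40%. The raw covariate was worse than none in 10 of 18 settings, for example at mean 4, shape 0.5: none 0.779, raw 0.857, log 0.702, so raw/none = 0.857/0.779 = 1.10. A separate run of 18 settings with 1,000 trials each gave cuts of 2-42%.

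**Step 4: the LSMean.** Write the log of the expected count as a + b(group) + c(x), where x is the baseline covariate. The LSMean is exp(a + b·group + c·mean x). The standardised mean is the average of exp(a + b·group + c·x) over all patients. By Jensen's inequality, the first is below the second whenever c is not zero and baselines vary. Their ratio, exp(c·mean x) / average of exp(c·x), is the same in both arms. It therefore cancels from the rate ratio exp(b), but not from a difference in counts.

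- Raw covariate, lognormal grid: median ratio 0.71-0.99, so 1-29% low. The gamma grid gave 4-34% low.
- Log covariate: median ratio 0.54-0.99, so 1-46% low. The gamma grid gave 4-57% low.
- Example (gamma shape 1, true control mean 5, correlation 0.9, raw covariate): LSMean 4.18 against standardised 5.12; 1 - 4.18/5.12 = 18% low. At a rate ratio of 0.6 the arm difference would read 4.18 × 0.4 = 1.67 rather than 5.12 × 0.4 = 2.05.

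**The case against.** **The sizes are assumed.** This stands. The simulated designs also act multiplicatively on patient rates, which favours a log-type covariate, and 0.5 is itself a choice. With weak correlation, the log form need not beat no adjustment: 0.506 against 0.496 at zero correlation, log-SD 1.0, mean 5.

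**The LSMean is what the plan says it is.** This also stands. It is a valid prediction for a patient at the mean baseline, and misleads only if presented as an arm mean.

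**Stronger readings that a reader might infer, and that are not supported:**

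- *The group comparison is biased by the covariate level.* It is not. With no baseline-by-group interaction, the level cancels from the rate ratio.
- *Raw adjustment is generally worse than none.* In the lognormal grid this occurs only at correlation 0-0.4, by at most 1.06-fold; at 0.9 the SD ratio is 0.77-0.89, a clear gain over none. The two problems also largely fall in different settings: at correlation 0-0.4 the raw-covariate LSMeans are only 1-5% low.
- *The log covariate raises power by a quotable amount.* Such figures would need an overdispersion-scaled test, which the plan does not state. With unscaled Poisson errors under no effect, a further simulation (800 trials per setting) gave false-positive rates of about 10-71% with the raw covariate and 10-66% with the log covariate. A power comparison has no meaning until that is dealt with.
- *The log covariate also cures the low counts.* It does not. Step 4 shows that the LSMean is generally further below the mean.

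**Conclusion.** The point holds as a minor refinement. Once the response is corrected to the follow-up count, a raw baseline count is a poor covariate form under a log link. Replacing it with log(baseline + 0.5) lowers the SD of the log rate ratio by about 0-40%, depending on skew, mean count and correlation. With weak correlation, the raw covariate can be slightly worse than no adjustment, typically by up to about 10% in SD. Per-arm counts taken at the mean baseline lie about 1-34% below the mean count with the raw covariate, and further below with the log covariate. The direction of the LSMean result is mathematical and is exact relative to the model's own standardised mean; chance baseline imbalance can move an observed arm mean either way. All sizes rest on assumed rates, skew and correlation. Only the additional hypoglycemia counts are affected, not the HbA1c primary outcome.

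**What to change.** In the Statistical Analysis section, for count outcomes:

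1. State that the response is the number of episodes at follow-up, not the change.
2. Enter log(baseline episodes + 0.5) as the covariate, with the constant fixed in advance.
3. If per-arm counts are reported as arm means, set every patient to each arm in turn, predict from that patient's own baseline, and average. Otherwise label the LSMean as the prediction at the mean baseline covariate value.
4. Keep the untransformed baseline for HbA1c.

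The cost is a few sentences and a few lines of code, on baseline data already collected from everyone. The downside is an arbitrary constant and possibly negligible gain at low counts. Overdispersion, on which the plan is silent, needs its own remedy and is not solved by this change.

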Approximately every three weeks, patients will have remote visits using the DAT clinic. HCPs obtained CGM and SIP data using software applications (as above). Trends of hyperglycemia and hypoglycemia and their relationship with insulin administration will be identified, leading to adjustments of diabetes medications (insulin or non-insulin). Communication will be done by VVC, SM, or by phone. Patients will be evaluated more (i.e., if acute changes are needed after hypoglycemic events) or less frequently (i.e. if no changes on medications are needed). At the last remote visit (+180 days), all patients will have repeat lab work of CBC, BMP, HbA1c, and urine creatinine/ microalbumin.

iii) Consultation (telecommunication) by an exercise physiologist (Days 0, +90 days, +180 days [end of RCT]):

On day 0, the exercise physiologist will evaluate baseline PA data and medical history, telecommunicate with each participant regarding their PA goals, facilitators, and barriers, and will write a PA prescription (frequency/intensity/duration/type) following best practices 64. On days +90 and +180, he will discuss progress, set motivational intermediate goals to reach the long-term PA prescription objectives, and will modify exercises as needed.

"Improving Glycemic Control in DM2 Patients in the Ambulatory Setting"

PI [name]
NCT04800471

iv) Research Visit: At +180 days (end of RCT):

Subjects will be placed on a "blinded" CGM. After ten days, Veterans will be asked to return the CGM, which will be downloaded. Subjects will complete the Senior Fitness test for PA evaluation.

Following the initial baseline visit, subjects in the SoC group will have the following interventions:

i) One in-person (Initial) Clinic Visit (Day 0):

This visit will be identical to the in-person visit that subjects will be randomized to the Telemedicine group had on Day 0.

ii) Two in-person Clinic Visits (Day +90, +180):

Subjects will have a typical clinic in-person visit. Vital signs and HbA1c will be obtained, physical examinations will be performed, and POC values (either by report, logbook, or glucometer) will be reviewed. Information regarding insulin use and adherence will be obtained through patient reporting. DM medication adjustments will be performed, and patients will be instructed to increase their PA as clinically indicated.

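### The model for primary HbA1c puts baseline rows into a change-score regression: as printed it halves the six-month effect; read as group × time it understates the standard error

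*Combined protocol and SAP*

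**What the plan says.** In the combined protocol and SAP, STATISTICAL ANALYSIS states one model for all outcomes, whatever the type of regression: "the model will be change in outcome= baseline value + group + time + group + time". The response is therefore a change from baseline. The time factor is then defined: "time will be baseline, three-month, or six-month". Continuous outcomes, including primary HbA1c, are to be fitted with "SAS proc genmod with a normal distribution and identity link". No REPEATED statement, subject effect or covariance structure is named. The next sentence reads "We will calculate estimated values at each time point using the mean value of the outcome at baseline", to be obtained with the "SAS LSMeans statement with a pdiff option".

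The HbA1c schedule is under Patient Population-Study Procedures. Both arms have HbA1c at day 0, because the SoC initial visit is described as identical to the telemedicine one. In the telemedicine arm the only listed follow-up value is at the end: "At the last remote visit (+180 days), all patients will have repeat lab work of CBC, BMP, HbA1c". For the SoC clinic visits at +90 and +180 days the text says "Vital signs and HbA1c will be obtained, physical examinations will be performed". The blinded CGM worn by both arms is placed at baseline and at +180 days.

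**The concern.** A change score at baseline is zero by construction in both arms. Making baseline a level of time adds 30 rows that have no outcome variance and no possible group difference. The printed formula repeats group and time and contains no product term, so it can be read in two ways.

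- **Literal.** One group effect is shared by all times. It averages the guaranteed zero at baseline with the follow-up difference, and LSMeans would show the same group difference at every time, including baseline.
- **Misprint for group × time.** The six-month contrast is then estimated separately and is not diluted. The residual variance is still pooled over all rows, and the zero-variance baseline rows pull it down, so the interval is too narrow and the p-value too small.

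This is the only model given for the primary outcome and the continuous CGM outcomes, and significance is declared at two-tailed P ≤ 0.05. The two readings distort the result in different ways, and the plan leaves the choice open until the data are seen.

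**Working it through.** **Inputs from the documents.** 30 patients, 1:1 (taken as 15 per arm); two-sided 0.05; HbA1c at day 0 and +180 (telemedicine) and at day 0, +90 and +180 (SoC). The plan gives no effect size, SD or correlation, so there is no stated figure to reproduce.

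**Assumptions.** SD 1.3; correlation 0.6 (range 0.4 to 0.8); true six-month difference d6 = -1.0 or -0.5; three-month difference d3 = 0.6 × d6; no dropout; least-squares scale with a t reference.

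**Rows on the listed schedule.** Telemedicine 15 × 2 = 30; SoC 15 × 3 = 45; total 75, of which 30 are baseline rows with change = 0.

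**Literal reading: size of the estimate.** The +90 rows come from SoC only and are absorbed by their own time level. The group coefficient is then the average of the group differences at the two times both arms share:

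(0 + d6)/2 = (0 - 1.0)/2 = -0.50, a fraction of 0.50.

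This does not depend on the SD or correlation. The fitted baseline changes are +0.25 (SoC) and -0.25 (telemedicine), although both are exactly 0. With baseline and six-month data only, the fraction is again 0.50. If both arms had all three times, it would be (0 + d3 + d6)/(3 × d6):

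- d3 = 0: 1/3 = 0.33
- d3 = 0.6 × d6: 1.6/3 = 0.53
- d3 = d6: 2/3 = 0.67

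**Group × time reading: size of the standard error.** The six-month contrast is -1.00 in every case. Only the non-baseline rows carry variance, so to a first approximation the model SE divided by the true SE is the square root of their share:

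- listed schedule: √(45/75) = 0.775
- baseline and six months only: √(30/60) = 0.707
- all three times in both arms: √(60/90) = 0.816

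Simulation gives 0.78, 0.73 and 0.83.

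**Operating characteristics** (10,000 simulated trials per setting; correlation 0.6, with the range over 0.4 to 0.8 in brackets):

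| Analysis | Result |
|---|---|
| Literal, listed schedule: 95% CI contains true -1.0 | 42% (17–55%) |
| Literal, listed schedule: 95% CI contains true -0.5 | 83% (69–87%) |
| Literal, listed schedule: false positives | 2% (2–3%) |
| Literal, listed schedule: power for -1.0 | 61% |
| Group × time, listed schedule: false positives | 12% (12%) |
| Group × time, baseline and six months: false positives | 15% (15–16%) |
| Group × time, all times: false positives | 10% (9–11%) |
| Six-month ANCOVA | coverage 95%, false positives 5%, power for -1.0 70% |

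Literal coverage falls as the correlation rises, because the interval narrows around an estimate that stays at half the truth.

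**Cause of the SE problem.** Dropping the baseline rows and keeping group × time on the listed schedule leaves 75 - 30 = 45 rows. The SE ratio becomes 0.97–0.98 and false positives 0.049–0.056 over correlations 0.3 to 0.7. The baseline rows, rather than the unmodelled within-subject correlation, are therefore the main cause for the six-month contrast.

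**Three-month contrast.** With HbA1c at +90 listed for SoC only, a group × time model cannot estimate a three-month HbA1c difference.

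**The case against.** The strongest reply is that the second plus sign is a typing or PDF-reading slip. Repeating the same two main effects does nothing, and LSMeans at each time point make sense only with an interaction. That is plausible. If so, the halved estimate, the poor coverage and the spurious baseline difference all fall away. The standard-error fault remains, because baseline is named as a time level in words and not by that symbol.

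A second reply is that two codings avoid most of the harm. An analyst might create change rows only after baseline, which restores the nominal error rate but departs from the time levels the plan states. Or GENMOD might be run with subject-clustered sandwich errors, which brings the group × time false-positive rate to about 7–8%. The plan does not mention them.

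Third, the 5% benchmark assumes a least-squares scale and t reference. With a maximum-likelihood scale and normal reference, six-month ANCOVA itself rejects in 7.2% of null trials, against 14.2% for group × time with baseline rows on the listed schedule. The excess remains, but the point is fair and the fix should name the scale and reference.

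Fourth, no outcome is listed at all three times in both arms, so those figures are only a sensitivity check. The shared blinded CGM is listed at baseline and +180, which puts the continuous CGM outcomes in the two-time case, where the SE understatement is largest.

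Finally, this is a 30-patient pilot with feasibility among its aims, and the literal reading does not inflate false positives. Both are true. The plan nevertheless makes HbA1c primary and sets a significance threshold, and the effect estimate is what a later trial would be designed on.

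**Conclusion.** The concern holds. Baseline should not be a level of time when the response is change from baseline, and neither reading of the formula is sound while those rows stay in.

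- **Literal reading:** the reported effect is 0.50 of the true six-month HbA1c difference. This follows from the listed schedule alone. The harm is mainly to the size of the effect, with some loss of power (61% against 70%).
- **Group × time reading:** the estimate is unbiased, but the standard error is about 78% of its true value and false positives are about 12% on the HbA1c schedule. For outcomes measured only at baseline and six months the figures are 73% and 15%.

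The coverage, power and error rates rest on the assumed SD, correlation and effects, on 15 per arm without dropout, and on model-based standard errors. The Poisson count outcomes were not computed and are outside this conclusion.

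**What to change.** State the primary analysis as ANCOVA: HbA1c at +180 days (or its change) = baseline HbA1c + group, reporting the six-month group difference with its 95% CI. Name the variance scale and reference distribution; a least-squares scale with a t reference holds the error rate near 5% at this sample size.

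For any outcome modelled longitudinally, restrict time to post-baseline visits measured in both arms, write the last term as group × time, specify the within-subject correlation, and report the six-month contrast. On the listed HbA1c schedule only +180 qualifies, so the model reduces to the ANCOVA above. The SAP should say that no three-month HbA1c comparison is planned, or the visit schedule and the three-month time level should be reconciled.

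The change to the analysis costs a few lines of SAP wording and code, with no new data, visits or patients.

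### The model of change names baseline and three months as time levels, but change at baseline is always zero and no modelled outcome is scheduled in both arms at three months

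*Combined protocol and SAP*

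**What the plan says.** The Statistical Analysis section prescribes normal-error regression for continuous outcomes and Poisson regression with a log link for counts. Both use the same formula: "Regardless of the type of regression we will use, the model will be change in outcome", printed in full as "change in outcome= baseline value + group + time + group + time". It adds that "time will be baseline, three-month, or six-month". On reporting, it says "We will calculate estimated values at each time point", using the "SAS LSMeans statement with a pdiff option". It gives no within-patient covariance structure and no time point for the primary HbA1c comparison. Significance is two-tailed at 0.05.

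The schedule is in Patient Population-Study Procedures. In both arms a blinded CGM is worn "for ten days to obtain baseline CGM glucose data". At the telemedicine Day 0 clinic visit, "CBC, BMP, HbA1c, and urine creatinine/microalbumin will be obtained per usual care", and the SoC Day 0 visit is identical. Telemedicine patients repeat HbA1c at +180. SoC patients have HbA1c at +90 and +180. The second blinded CGM wear is at +180 in both arms. Between visits telemedicine patients use CGM for treatment, while SoC patients use fingersticks.

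**The concern.** Two of the three time levels cannot do the work the model gives them.

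- **Three months.** One arm has no scheduled measurement of the primary outcome, and neither arm has a blinded CGM. Treatment CGM in the telemedicine arm has no SoC counterpart.
- **Baseline.** The response is a constant zero. These rows say nothing about treatment, but they still enter the fit and affect either the residual variance or the group coefficient.

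The formula also prints group plus time twice. The second occurrence is probably a misprinted group-by-time interaction, but that is not certain, and the two readings damage the six-month result in different ways. Extending the change formula to counts creates a further problem: a Poisson likelihood does not admit negative values, and a patient with fewer episodes at follow-up than at baseline has a negative change.

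At stake is the primary HbA1c result, either its error rate or its size, in a trial of 30 patients that will declare significance at 0.05.

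**Working it through.** The plan gives no numerical figure to reproduce on this point.

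**Step 1: schedule grid** (Patient Population-Study Procedures).

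| Outcome | Arm | Baseline | +90 | +180 |
|---|---|---|---|---|
| HbA1c | Telemedicine | yes | none listed | yes |
| HbA1c | SoC | yes | yes | yes |
| Blinded CGM | Telemedicine | yes | none | yes |
| Blinded CGM | SoC | yes | none | yes |

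With 30 patients at 1:1, planned HbA1c at +90 is 0 of 15 in telemedicine and 15 of 15 in SoC. Planned blinded CGM at +90 is 0 of 30.

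**Step 2: estimability, interaction reading.** HbA1c rows: 30 at baseline + 15 at +90 + 30 at +180 = 75. Columns: intercept, group, two time, two interaction, baseline value = 7. The rank is 6. The three-month group contrast is not estimable; the six-month contrast is. For blinded CGM there are 60 rows and the rank is 5 of 7, with no three-month data at all.

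**Step 3: standard error at six months, interaction reading.** Assumptions not in the documents: SD 1.3, correlation 0.4 to 0.8 between visits, no treatment effect, rows treated as independent, maximum-likelihood scale, Wald test. There were 8,000 simulated trials per setting.

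| Correlation | Mean SE | True SD | Type I, baseline rows kept | Type I, +180-only fit |
|---|---|---|---|---|
| 0.4 | 0.350 | 0.454 | 0.134 | 0.077 |
| 0.6 | 0.296 | 0.387 | 0.139 | 0.071 |
| 0.8 | 0.216 | 0.288 | 0.147 | 0.075 |

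As a check on the true SD at correlation 0.6, the residual SD is 1.3 × √(1 − 0.6²) = 1.04, and 1.04 × √(2/15) = 0.380. This is close to the simulated 0.387; the small excess comes from forcing one baseline slope on all time levels. The estimate is unbiased. Its SE is too small because the zero rows pull down the pooled variance.

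Variations for HbA1c at correlation 0.6:
- t tests instead of Wald: 0.116 against 0.047.
- SD 1.0 or 1.8 (4,000 runs): 0.143 or 0.142.
- Three per arm missing at +180: 0.157 against 0.085.
- Patient-clustered robust SE (4,000 runs): mean SE 0.368, true SD 0.383, type I error 0.066.

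Continuous CGM outcomes, at correlations 0.4/0.6/0.8: 0.172/0.180/0.190 against 0.077/0.072/0.074.

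**Step 4: additive reading, normal model.** A single group coefficient averages the group differences across time levels, with weight nT × nS / (nT + nS):
- baseline: 15 × 15 / 30 = 7.5, where the difference is zero;
- three months: 0 × 15 / 15 = 0;
- six months: 15 × 15 / 30 = 7.5.

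The six-month share is 7.5 / 15.0 = 0.50, so a true -0.80 becomes -0.40. Simulation gave -0.402, against -0.805 for the +180-only fit. With 12 per arm at +180 the weight is 12 × 12 / 24 = 6.0, the share is 6.0 / 13.5 = 0.44, and the estimate is about -0.36. A three-month difference would be printed, but it would be borrowed entirely from the other time levels.

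**Step 5: counts.** The documents give no event rate. For illustration, if visit counts are independent Poisson with the same mean at both visits, the change is negative in 35%, 42% and 44% of patients for means of 1, 3 and 6. The halving in Step 4 does not carry over to the log-link model.

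**The case against.** The best defence is that the harm is conditional. HbA1c at Day 0 and +180 exists in both arms, the six-month contrast is unbiased under the likelier reading, and a sensible analyst would drop the baseline rows or add a repeated-measures statement. The section does not say that rows are independent; that is inferred from its silence. The inflation and the halving belong to different readings and cannot both occur. Under the additive reading type I error is not raised (0.038 in one simulation), though power falls to 0.45 from 0.60. Part of the 0.14 belongs to the Wald test, since the +180-only fit already gives 0.07. A non-estimable contrast and a negative Poisson response would show themselves. This is also a pilot with a convenience sample.

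Much of this is fair. Leaving out the baseline rows removes the inflation and the dilution, and clustered errors largely restore the error rate. But the section specifies neither, and it names baseline as a time level outright. Neither remedy supplies a telemedicine HbA1c at +90 or makes change a valid Poisson response. The t-test comparison (0.116 against 0.047) shows that the baseline rows matter apart from the Wald test. The negative-count percentages are illustrative only; the point stands without them. Pilot status lowers the stakes, but the trial still names a primary outcome and a significance threshold.

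**Conclusion.** The concern holds and needs correcting before analysis. Three facts do not depend on any assumption: no modelled outcome is scheduled in both arms at +90, change at baseline is zero by definition, and change in a count can be negative. The three-month contrast is therefore unsupported for every outcome, and the count model cannot be fitted validly as written.

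The damage to the six-month result depends on how the formula is read and on baseline rows being entered:
- **Interaction, rows independent:** type I error 0.13-0.15 for HbA1c and 0.17-0.19 for continuous CGM outcomes, against 0.07-0.08 for a +180-only fit.
- **Additive:** about half the true six-month effect for normal-model outcomes, including primary HbA1c.

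These sizes rest on 15 per arm, correlation 0.4-0.8, and the Wald test for the error rates. They change little with the SD. If baseline rows are left out, only the three-month and count defects remain. The schedule implies +180 as the primary time point, but the plan does not name it.

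**What to change.** Name change in HbA1c at +180 days as the primary comparison. Remove baseline and three months as outcome time levels. Model each continuous outcome as the +180 change on group plus baseline value, with one row per patient. Model each count as the +180 count on group plus baseline count. Report SoC HbA1c at +90 descriptively. With about 30 patients it is also worth stating a t or F reference for the continuous models, because the maximum-likelihood Wald test alone gives 0.07-0.08.

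This costs SAP wording only. It gives up a three-month between-arm result, which the schedule cannot support.

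If a three-month contrast is wanted, the same outcome must be measured in both arms at +90, the interaction written out, baseline rows excluded and within-patient correlation modelled. That alternative adds a measurement and so changes the visit schedule.
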